10. HUMAN SUBJECTS

Total number of participants to be enrolled: This will be a single site study with 120 participants enrolled at UCSD.

Age: Because of the problems inherent in the use of cannabis in children and adolescents, we will not enroll individuals below the age of nineteen. Frequent use can affect school performance and relationships with family members in younger individuals ^{42, 43}. Earlier and greater involvement with marijuana has also been associated with increased risk of poor mental health ^{44, 45}.

Gender: Both male and female populations develop chronic low back pain (CLBP); however, there is a tendency towards a higher incidence in males.

Ethnic background: CLBP is ubiquitous. Global studies have shown that low back pain is one of the most common complaints that patients bring to their physicians ^{46, 47}. Given the diverse ethnic background of San Diego, we should be able to recruit subjects from multiple ethnic backgrounds. A neuropathic component has been found in approximately 37% of patients with CLBP ⁴⁸; given the relative frequency of the latter, we should not encounter difficulty recruiting 120 participants.

Health status: Individuals with significant cardiovascular, hepatic or renal disease, uncontrolled hypertension, and chronic pulmonary disease (eg, asthma, COPD), will be excluded. This will be operationalized using criteria from the literature on adverse effects of medicinal cannabis ^{49, 50}.

Inclusion criteria

- Age greater than 18
- Presence of chronic low back pain (CLBP) defined as the response to two questions 1) How long has back pain been an ongoing problem for you? 2) How often has low back pain been an ongoing problem for you over the past 6 months? A response of greater than 3 months to question 1 and a response of "at least half the days in the past 6 months" to question 2 will define CLBP according to the NIH Task Force on Research Standards for Chronic Low Back Pain (Appendix 15). ⁹
- Visual average numerical pain intensity greater than 3/10 during one-week observation period
- To avoid confounding by concurrent medications and/or prior cannabis exposure, participants will have had a stable analgesic regimen that they will continue throughout the study and not having used cannabis for more than 7 days prior to study entry. The latter criteria will be verified by the use of the Draeger test at the first experimental visit.

Exclusion criteria

- Presence of another painful condition of greater severity than the back pain condition which is being studied.
- History of traumatic brain injury.
- Clinically significant or unstable medical condition. Individuals with significant cardiovascular, hepatic or renal disease, uncontrolled hypertension, and chronic pulmonary disease (eg, asthma, COPD), will be excluded. With respect to cardiovascular and pulmonary status, a clinician will screen participants with a tool developed for detection of congestive heart failure, coronary artery disease, obstructive and/or restrictive lung disease (Appendix 28 Cardiopulmonary Screen). Hepatic and renal disease will be evaluated with liver and renal function laboratory tests. If warranted clinically, subjects will undergo further evaluation (urinalysis, electrocardiogram, and/or chest X-ray).
- A positive result on toxicity screening will exclude individuals from participation. A urine drug test that screens for 5 categories of drugs: marijuana ($\Delta 9$ -THC), cocaine, amphetamines/methamphetamines, opiates, benzodiazepines and phencyclidine (PCP) will be employed. A positive result for opioids and/or THC will not be exclusionary if the patient is receiving a prescription for an opioid and/or THC.
- Allergy to sesame oil, lactose, or gelatin
- Vascular disease, especially Raynauld's syndrome, systolic blood pressure > 170 mm, diastolic blood pressure > 100 mm
- Recent injuries to the upper extremity
- Cognitive impairment, such as Dementia or Alzheimer's Disease
- Substance Abuse History: individuals with current substance use disorders⁵⁵ as assessed using the Drug Abuse Screening Test (DAST-10) (a score greater than or equal to 3) and the Alcohol Use Disorders Identification Test (AUDIT) (a score greater than or equal to 8 or a score greater than or equal to 7 if over 65 years old) (Appendix 31).
- Pregnancy as ascertained by a mandatory commercial pregnancy test
- Women who are lactating
- History of schizophrenia, bipolar depression with mania, current suicidal ideation or past history of suicide attempt. Cannabis can exacerbate pre-existing schizophrenia, and has been linked to an increase in the risk of suicide in such patients.⁵⁶ In patients with bipolar disorder, cannabis use has been associated with worsening of manic and psychotic symptoms.⁵⁷ Such findings suggest that cannabis is contraindicated in individuals with serious mental health issues, a line of reasoning that will be observed in the present study by excluding patients in the bipolar/schizoaffective/schizophrenic spectrum.
- Suicidality. Exposure to cannabis does not lead to depression but it may be associated with suicidal thoughts and attempts⁵⁸. Therefore, the BDI-II will be used to measure suicidal ideation.
- Unwillingness to abstain from dronabinol for the rest of the study if taking dronabinol before study participation.

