If already using cannabis, participants will be asked to slowly taper cannabis use over a one-week period (Baseline Week - Figure 1) so that they are only using study medications during the remaining 10 weeks of the clinical trial. If unable to abide by this, subjects will not be allowed to participate in the study. Participants will be asked to abstain from cannabis 7 days prior to study entry. In order to ensure abstinence, we will use the Draeger 5000 saliva screening test for tetrahydrocannabinol at their first experimental visit to ensure that they have adhered to this period of abstinence before the study. A level above 5 ng/ml will indicate recent use and the appointment will be rescheduled.

Baseline Period:

If eligibility criteria (see below) are met, subjects will be instructed on completing a paper diary (Appendix 4). Provided their VAS pain intensity remains above 3/10 during the Baseline Week, they will be given oral and herbal study medication (and a Volcano Vaporizer) at the next study visit one week later.

At the baseline visit, participants will be given the Beck Depression Inventory (BDI-II) in order to screen for depression and suicidality. They will also be given the AUDIT and DAST to screen for substance use problems. The PSQ and Mood Disorder Questionnaire will also be administered to screen for Schizophrenia and Bipolar Type I, respectively. The painDETECT Questionnaire will be administered to distinguish neuropathic low back pain from non-neuropathic low back pain. The Survey of Cannabis Use will be administered during this period to obtain information on the cannabis use habits of the participant.

Should the participant choose to participate in the driving simulation portion of the study, the Driving History and Habits Questionnaire will be administered to obtain information on participant driving history, should they decide to participate in the driving simulation study portion.

Telephone Interview:

To determine eligibility, each prospective participant will be asked the following questions from the NIH Chronic Low Back Pain Definition:

1. Do you have low back pain?

No	STOP.....	0
Yes		1

2. How long has low back pain been an ongoing problem for you?

Less than 1 month	0
1-3 months	1
3-6 months	2
6 months -1 year	3
1-5 years	4
More than 5 years	5

3. How often has low back pain been an ongoing problem for you over the past 6 months?

[figure not shown]
Every day or nearly every day in the past 6 months	0

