Subjects will be instructed on the use of a vaporizer at the visit prior to Week 1. The manufacturer's instructional brochure (Appendix 6) will be reviewed. In order to ensure consistency of dosing throughout the study, they will also be instructed on the use of the Foltin puff procedure at the visit prior to Week 1 (Appendix 7). A copy of both of these documents will be provided for review at home.

On completion of eight weeks of treatment or at the time of withdrawal from the study, patients will completely taper their cannabis over a period of one to two weeks to avoid withdrawal symptoms. Cannabis withdrawal symptoms will be measured via a phone call after Taper weeks 1 and 2 (Appendix 8). Questions (Appendix 26) will be added to access subject's beliefs of what they received (e.g., THC or placebo) after the first week and again after the eighth week. This will enable us to assess the effectiveness of blinding and thus report on the assay sensitivity of the study. The optimal

timing and frequency of blinding assessments has not been established. Thus, we will use a strategy to collect blinding data two times from participants: shortly after randomization and at the end of the trial. This will permit a comparison of blinding at the two stages.

If a subject does not participate in the driving simulation or the microbiome substudy, we will test their oral fluid for the presence of THC using the Draeger 5000. This will be done to exclude participants who use their own cannabis seeking pain relief because they were given placebo.

An online questionnaire will be deployed (Appendix 27). Potential participants will complete this using HIPAA compliant software, the Platinum Edition of Survey Monkey. Please see <https://www.surveymonkey.com/pricing/details/> for verification of the HIPAA compliance of this survey.

Outcome Measures:

DAILY TESTING IN SUBJECT'S RESIDENCE USING PAPER DIARY

Medication intake: The timing and number of puffs of vaporized cannabis or placebo THC), oral medication (dronabinol or placebo), and breakthrough pain medication will be chronicled. (5 minutes)

REPEATED TESTING AT STUDY VISITS

Center for Medicinal Cannabis Research Forms

- Neurobehavioral Medical Screen: The clinician will fill this out to record any events that may have occurred between visits to confound results from the Neuropsychological testing such as an any trauma to the head or any open head wounds.

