- Behavior Notes Instrument: The clinician will fill this out during Neuropsychological testing to note confound variables associated with participant during the appointment.
- Adverse Events Form: A form to be filled out by the clinician that records any adverse events that have occurred since the last appointment due to study medication.

NIH Task Force on CLBP Impact Score

The impact score is a novel combination of 3 constructs; pain intensity, interference, and function. It is assembled in the Repeated Measures Recommended Minimal Dataset (Appendix 9).⁹

Pain Relief

Neuropathic Pain Scale: This instrument has an ordinal scoring of one to ten for several characteristics of neuropathic pain.^{10, 11} Specifically, the responses measure pain characteristics such as intensity, sharpness ("like a knife"), burning ("on fire"), aching ("like a bruise"), cold ("freezing"), sensitivity ("like raw skin"), itching ("like poison oak"), unpleasantness ("intolerable"), and the amount of deep versus superficial pain. (5 minutes)

Mood Evaluation

Profile of Mood States (POMS): The POMS measures six identifiable mood or affective states: 1) Tension-Anxiety 2) Vigor-Activity 3) Depression-Dejection 4) Fatigue-Inertia 5) Anger-Hostility 6) Confusion-Bewilderment. The POMS can be re-administered on a weekly basis, which is long enough to detect the respondent's mood responses to his or her current life situation, but short enough to assess acute treatment effects. Sixty five items rated from 0 to 4 and scored in terms of total mood disturbance.¹² (10 minutes)

Beck Depression Inventory-II (BDI-II): The BDI-II is a twenty-one item depression scale in which participants can rate depressive symptoms and attitudes from 0 to 3 in terms of intensity.¹³ We will measure clinical depression using the BDI-II and will include this measurement in analyses to provide an adjusted view of analgesia and side-effects. (3 minutes)

Neuropsychological Testing

WAIS-III Digit Symbol test: a test of concentration, psychomotor speed, and graphomotor abilities. This pen and paper test involves having subjects substitute a series of symbols with numbers as quickly and accurately as possible during a 120 second period. The results are expressed as the number of correct substitutions.¹⁴ (10 minutes).

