4.2 Secondary endpoints

The secondary outcomes include the level of use of breakthrough pain medication, pain tolerance and sensitivity, chronic low back pain (CLBP) impact score, neuropathic pain scale (NPS, a sum of 10 pain descriptors), profile of mood states (total mood disturbance scores), Beck Depression Inventory II, ability to learn and recall measured using Hopkins Verbal Learning Test (HVLT), measures of concentration, psychomotor speed, and graphomotor abilities by Wechsler Adult Intelligence Scale -III (WAIS-III) digit symbol test, marijuana subscale (M-scale), motor coordination and speed evaluated by grooved pegboard test. In addition, subjective and psychoactive side effects (e.g., good drug effect, drug high) and measures (e.g., lane tracking, car following) in driving simulation will be examined as secondary outcomes in a substudy, where completers with a valid driver's license will receive acute administration of treatment at the driving simulation visit.

All comparisons of secondary outcomes between arms will be with an order of importance as described above for the primary endpoint: 1) primary comparison: arm A vs. arm B; 2) secondary comparison: arm A vs. arm C; exploratory comparison: arm B vs. arm C. No correction will be done for multiple comparisons.

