4.2.1 Comparison of outcomes measured at 6 visits between treatment arms

The similar analysis strategies as described above for primary endpoint will be used for the secondary outcomes measured at 6 visits. Briefly, the interaction effect of treatment arm and time (6 visits) on outcome will be tested using a covariance pattern model (e.g., unstructured model). Average change at the treatment period (weeks 5-8) from baseline will be compared between the groups. Non-significant interaction terms will be removed from the models (Aim 2).

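### The SAP analyses the BDI-II only through means, which cannot show a few new cases of suicidal ideation, and no visible rule carries such an answer into the adverse event tables; a by-arm count is needed.

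*Protocol*

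**What the plan says.** - **Reason for measuring suicidality.** Protocol section 10, in the exclusion criteria, says of cannabis exposure that "it may be associated with suicidal thoughts and attempts", and continues: "Therefore, the BDI-II will be used to measure suicidal ideation". The preceding criterion already excludes current suicidal ideation and any past attempt.
- **Baseline screen.** Protocol section 9, Baseline Period: "participants will be given the Beck Depression Inventory (BDI-II) in order to screen for depression and suicidality".
- **Repeat use.** The BDI-II also appears under the section 9 heading "REPEATED TESTING AT STUDY VISITS". Its description there begins "The BDI-II is a twenty-one item depression scale in which participants can rate depressive symptoms and attitudes from 0 to 3". The purpose given is different: "We will measure clinical depression using the BDI-II and will include this measurement in analyses to provide an adjusted view of analgesia and side-effects".
- **SAP endpoint.** SAP 4.2 lists the instrument among the secondary outcomes, next to the mood scale: "profile of mood states (total mood disturbance scores), Beck Depression Inventory II". It names no single response and no threshold.
- **SAP analysis.** SAP 4.2.1 tests the arm-by-time interaction over the six visits in a covariance pattern model, and adds: "Average change at the treatment period (weeks 5-8) from baseline will be compared between the groups". Mood may also enter the mediation model in SAP 4.3.3.
- **Safety reporting.** SAP 3.1 tabulates participants with adverse events by arm and grade. SAP 6.1 and 6.2 list adverse event type, severity and counts for the DSMC. None of these has a line for suicidal ideation.

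**The concern.** The protocol's reason for measuring suicidal ideation is a possible effect of exposure. A baseline screen cannot monitor that, whereas the repeated BDI-II could. Because people with current ideation or a past attempt are excluded, reports after baseline should be largely new and easy to interpret.

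The planned BDI-II analyses all work on means, and a rare response from a few participants does not move a mean of 21-item totals. The weeks 5-8 contrast also leaves out titration. Participants who cannot tolerate the minimum dose are dropped by the end of week 4 and replaced (SAP section 1), so they have no weeks 5-8 value.

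At stake is the risk-benefit assessment promised in Protocol section 5. The trial could report a favourable mean BDI-II change by arm without stating how many participants reported suicidal thoughts on treatment.

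**Working it through.** **Inputs.** From SAP 5.1: 40 randomised per arm, 16% dropout, 33 per arm for Aims 1 and 2, 5% significance, 80% power, detectable d = 0.54 (d = 0.58 at 29 per arm). From SAP 4.1.1: time points 0, 1, 3, 5, 7 and 8 weeks. From Protocol section 9: 21 items scored 0 to 3, so a maximum of 63. Assumed, because the documents do not say: BDI-II SD of 6 to 10, within-person correlation of 0.5, two-sided testing, and one response scored 0 to 3 that carries suicidality.

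**1. The plan's detectable effect.** For a time-by-treatment slope, d = (1.960 + 0.842) × √(2/n) × √[(1 − ρ) × T² / Σ(t − mean t)²]. Here T = 8, mean t = 4 and Σ(t − 4)² = 16 + 9 + 1 + 1 + 9 + 16 = 52, so T²/52 = 64/52 = 1.231.
- n = 33, ρ = 0.5: 2.802 × 0.2462 × √(0.5 × 1.231) = 0.541.
- n = 29, ρ = 0.5: 2.802 × 0.2626 × 0.7845 = 0.577.

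Both match the SAP. On the BDI-II total, d = 0.54 is 0.54 × 6 = 3.2 to 0.54 × 10 = 5.4 points.

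**2. What new ideation does to an arm mean.** Shift = cases × item change / 33, with the other 20 items unchanged.
- One case, 0 to 1: 1/33 = 0.03 points.
- One case, 0 to 3: 3/33 = 0.09 points.
- Three cases, 0 to 1: 3/33 = 0.09 points.
- Five cases, 0 to 3: 15/33 = 0.45 points, or d = 0.45/10 = 0.045 to 0.4545/6 = 0.076.

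The standard error of an arm difference is SD × √(2/33): 1.48, 1.97 and 2.46 points for SD 6, 8 and 10. One maximal case is 0.091/1.48 = 6% of a standard error at SD 6 and 0.091/2.46 = 4% at SD 10. Under a simple two-sample comparison, five maximal cases give a 3.8% to 4.9% chance of significance in the direction of harm, against 2.5% with no effect at all.

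A person with new ideation may worsen on other items too. As an illustration, a 20-point rise in one participant's total moves the arm mean by 20/33 = 0.61 points, still 0.61/1.48 = 0.41 of a standard error at SD 6.

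**3. What a count would show.**
- Chance of at least one case among 33, 1 − (1 − p)³³: 49%, 82% and 97% for true rates of 2%, 5% and 10%.
- Upper limit with 0 of 33: 1 − 0.05^(1/33) = 8.7% (one-sided 95%); 1 − 0.025^(1/33) = 10.6% (two-sided 95%).
- Fisher's exact test, 33 per arm: 3 v 0, p = 0.24; 5 v 0, p = 0.053; 6 v 0, p = 0.024.

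The count makes cases visible and bounds the rate. It is not a powered test.

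**4. Whether another route ensures reporting.** The visit Adverse Events Form (Protocol section 9) covers events attributed to study medication. Section 15 has the form completed from a solicited instrument, given as needed and routinely at the end of the acute session. The items described there are anxiety, paranoia, hallucinations, dizziness, drowsiness, confusion, and emotional and cognitive changes; suicidal ideation is not among them. No text turns a BDI-II answer into an adverse event. The evaluation step for disclosed ideation, in section 16, sits in the account of the consent process.

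**The case against.** A reader might infer that the protocol commits to the BDI-II as an on-treatment suicidality endpoint, and that the plan would hide such cases from the DSMC. The documents support neither.

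- The sentence naming the BDI-II is an eligibility criterion, and section 9 ties the suicidality screen to baseline. Where the instrument is repeated, the stated purpose is clinical depression and adjustment, and a score-based analysis fits that purpose. This stands.
- Nor does the SAP look only at weeks 5-8. The interaction test uses all six visits, though it too compares means.
- An adverse event route exists. Clinicians complete a form at visits, the solicited instrument asks about emotional changes, Grade 2 to 4 responses go to a study clinician, and SAP 3.1 and 6.2 report events by arm. Section 15 also has the investigator judge relatedness, including unrelated, so the form's limit to drug-related events may not be strict in practice. The DSMC lists name no individual event term, so the absence of suicidal ideation does not show that it is excluded.
- Appendices 18, 29 and 30, on suicidal ideation and the adverse event instruments, were not available and may close part of the gap.
- Counts would be small and a test weak, as the working shows.

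These points limit the claim to this: reporting is possible but not assured. They do not supply the missing summary or the missing link from a BDI-II answer to adverse event reporting.

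**Conclusion.** The point holds in this form. The protocol links cannabis to suicidal thoughts, names the BDI-II as its measure of ideation and repeats it on treatment, but the SAP contains only mean-level analyses of it. Those cannot show a few cases: one to five new cases move an arm mean by 0.03 to 0.45 of 63 points, at most d = 0.08 against a detectable 0.54. Nothing in the available text ensures that a positive on-treatment answer reaches the adverse event tables or the DSMC.

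The size rests on the assumed SD of 6 to 10 and on a change confined to one response. The conclusion is not sensitive to either within the ranges shown. It could change if the unavailable appendices already route BDI-II answers into adverse event reporting. The change is worth making for safety reporting; it does not affect the primary analysis.

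**What to change.** - Add to SAP 3.1, and to the safety section of the closed report in SAP 6.2, the N (%) by arm of participants with any post-baseline suicidal ideation on the BDI-II response used for screening. The SAP should name that response and the scoring rule.
- Count all post-baseline visits. Include participants dropped or replaced by week 4, with every participant who has a post-baseline BDI-II in the denominator.
- Report it descriptively with exact confidence intervals. Fisher's exact test is optional and has little power.
- State whether a positive BDI-II answer on treatment is also recorded as an adverse event.
- Read Protocol sections 10, 15 and 16 together and clarify whether the evaluation described in section 16 applies to BDI-II answers given on treatment. The clinical action is for the investigators; none is proposed here.

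The cost is SAP wording and one row in each of two tables, from data already collected. The downside is small counts that cannot support a formal comparison and should not be presented as one.

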11. RECRUITMENT AND PROCEDURES PREPARATORY TO RESEARCH

Four methods will be used for patient recruitment. First, a UCSD clinician may ask patients directly if they are interested in the study. For example, a UCSD Center for Pain Medicine clinician can provide interested patients with an information sheet about the study, including research staff contact information (Appendix 1). Second, we will use ResearchMatch to send a recruitment message to potential participants who meet the criteria specified. (Appendix 3). Third, newspaper advertisements

will be utilized (Appendix 2). Fourth, ICD-9 code 724.2 will be used to identify pertinent potential subjects. The following PHI will be requested: patient name, mailing address, date of birth. This request (along with documentation of UCSD IRB approval) will be forwarded to database managers at the Clinical Data Warehouse for Research (CDWR) who will be asked to pull a subset of the data from the Electronic Health Record system to query patient information in a HIPAA-compliant manner. All recruitment methods will rely on potential subjects voluntarily initiating contact with study research staff.

Data Mining

HIPAA Access to personal health information (PHI) will be requested through a waiver of consent and partial waiver of HIPAA Authorization for recruitment purposes. In order for a partial waiver of HIPAA authorization to be granted, we present the following options:

1 A plan to protect identifiers from improper use and disclosure

Multiple procedures for protecting against or minimizing risks will be put in place. All research staff will complete training for HIPAA and human subjects' protections regulations and procedures. Confidentiality of participant data will be maintained through several mechanisms. All participants will be assigned identification numbers, and a list linking names and ID number will be stored separate from participant data in a locked file cabinet and electronically on a secure server. Access to this list will be restricted to the principal investigator, project manager and research assistant. Blood specimens will be stored in a -70 degree freezer using the ID number.

Paper documents will be kept in a locked cabinet in the CMCR office on [name]. Electronic information will be stored in a password-protected account.

2. Justification as to why these procedures could not a) practicably be done without the waiver, and b) be done without access to, use, or disclosure of the PHI;

The proposed study cannot be done without the specified information because PHI is required in order to contact potential participants and screen for eligibility for the study. We will only collect minimal PHI necessary to distinguish patients who have chronic lower back pain who may qualify for the study. Once they have been identified, patients who agree to participate in the study will be consented and authorization will be obtained.

3. Justification that the privacy risk to individuals whose PHI will be used or disclosed is minimal and reasonable in relation to the anticipated benefit, if any, to the individuals;

PHI acquired for the purposes of recruitment will not be disclosed to any other agency, party or individual (other than the sponsor (NIDA), FDA and UCSD research compliance personnel). Evidence of UCSD IRB approval will be required to obtain this document from NIDA.

4. What PHI will be used and who will access, use or disclose the PHI. ICD-9 code 724.2 will be used to identify pertinent potential subjects.

The following PHI will be requested: patient name, mailing address, date of birth. This request (along with documentation of UCSD IRB approval) will be forwarded to database managers at the Clinical Data Warehouse for Research (CDWR) who will be asked to pull a subset of the data from the Electronic Health Record system to query patient information in a HIPAA-compliant manner.

 History and Physical Exam	 Progress Notes
 Operative Report(s)	 Discharge Summary(ies)
 Diagnoses	 Medications
 Radiology Images	 Radiology Reports
 Pathology Reports	 Laboratory Reports
 EKG Reports	 Consult Reports
 Alcoholism or Alcohol Use	 Drug Abuse Information

Only authorized members of the research team will have access to PHI, specifically the principal investigator, project manager, and research associate/assistant.

